3.0 Objectives

Our overarching hypothesis is that MyPath will increase patient-centered reproductive planning discussions and improve contraceptive decision quality, leading to improved reproductive behaviors and health outcomes for women Veterans receiving primary care at VA. To test this hypothesis, we will conduct a randomized controlled trial (RCT) at up to 16 sites, clustered at the provider level among up to 100 providers and their reproductive-aged women Veteran patients, guided by the following aims:

Aim 1. To test the effect of MyPath on the occurrence of reproductive planning discussions with SDM (primary outcome), compared to usual care. Secondary outcomes include the impact of MyPath on communication self-efficacy and measures of contraceptive decision quality (knowledge, decisional conflict, values concordance).

Aim 2. To test the effect of MyPath on clinical outcomes at 3 and 6 months after the index visit including contraceptive utilization (continuous contraceptive use, use of effective methods) and unintended pregnancy, compared to usual care. Exploratory outcomes will include behaviors to modify preconception health risks.

Aim 3. To identify potential barriers and facilitators to implementation by collecting process and cost data and conducting qualitative interviews with Veterans, providers, and clinic leaders, with the goal of facilitating future implementation in partnership with Women's Health Services if MyPath is found to be effective.

Exploratory analyses will also look for effect modification of Aim 1 and 2 outcomes by race/ethnicity, age, visit modality (in-person or virtual) and provider practice-type (Women's Clinic or non-Women's Clinic).

In addition, we plan to obtain covariate and outcome data in VA Corporate Data Warehouse (CDW) from the electronic health record to collect some demographic and covariate variables and inform future implementation studies. We will compare self-reported reproductive health outcomes of participants (collected at 3- and 6-months) with reproductive health data from the

electronic health record to assess for agreement and identify possible CDW structured data that would be used as outcomes for larger-scale implementation studies.

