
Please complete this survey for “Improving Outcomes for Women Veterans”:
 
[Link to Qualtrics Survey]
 
Questions? Call 206-XXX-XXXX

Reminder: Submit your next survey to help improve women Vets’ healthcare:
 
[Link to Qualtrics Survey]
 
Questions? Call 206-XXX-XXXX

Reminder: Submit survey to support women’s health at VA and receive \$50:
 
[Link to Qualtrics Survey]
 
Questions? Call 206-XXX-XXXX

Please complete VA women’s health study survey by MM/DD to receive \$50:
 
[Link to Qualtrics Survey]
 
Questions? Call 206-XXX-XXXX

Reminder: Help the VA improve care for women Vets and receive \$50:
 
[Link to Qualtrics Survey]
 
Questions? Call 206-XXX-XXXX

All survey questions assessed at each timepoint are provided in the attached Patient Survey Instruments (Attachment Q) and summarized below.

- Baseline survey: Demographics, pregnancy intentions, and whether the patient is at risk of unintended pregnancy (UIP) will be assessed. Baseline preconception health risks will be assessed.
- Post-visit survey: The primary outcome of the occurrence of a reproductive planning discussion with SDM and the secondary outcomes of communication self-efficacy and family planning knowledge will be assessed among all participants. Secondary outcomes relating to contraceptive choices and decisions will also be assessed post-visit among the subgroup at risk of UIP. Whether participants discussed preconception health risks or received any services related to preconception health risks identified at baseline will be assessed among participants considering pregnancy. At the end of the post-visit survey we will ask questions related to use of the intervention for Aim 3, including collecting the users’ assigned personal codes as described above.
- 3- and 6-month surveys: Changes in pregnancy goals and whether the patient continues to be at risk of UIP will be assessed. Secondary outcomes relating to contraceptive use and unintended pregnancy will be assessed among the group remaining at risk of UIP. Preconception health behaviors, an exploratory outcome, will be assessed.

Aim 3 Qualitative Interview: Intervention arm patients who participate in the qualitative interview will be asked questions about their experience receiving the MyPath text message, using or not using the MyPath intervention, and using any other similar health-related tools previously (see interview guide, Attachment S).

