5.6 Data Analysis

Aims 1 and 2 - Sample Size:

Sample size and power calculations are based on our primary outcome, occurrence of reproductive planning discussion between patient and provider with shared decision making (SDM), and rely on formulas specified for use in cluster randomized trials accounting for non-use of the tool in the intervention group and attrition.[39] We estimate that the baseline prevalence of discussions of contraception and/or preconception health among women who could potentially become pregnant will be 50%, based on estimates from the nationally-representative VA ECUUN study and our pilot study.[2] Based on field testing, we estimate that 30% of women participants enrolled in the intervention arm who receive the text with the MyPath link will not actually view the tool and the sample size calculation will thus account for this estimated non-use. Assuming a kappa coefficient of 0.01 and attrition of 5%, a sample of 456 patients (approximately 15 patients for each of 30 providers) will yield 80% power in 2-sided tests with a type-1 error rate of 5% to detect a 20-percentage point increase in reproductive planning with SDM to 70%. This difference is clinically meaningful and consistent with what we observed in our pilot (22% increase).

Aims 1 and 2 - Missing data and subject dropouts:

For the 3- and 6-month follow-up periods, we assume 20% attrition (15% lost to follow up and 5% who either become pregnant or change to desiring pregnancy). This is a conservative estimate based on 7% attrition at 3-months in our pilot. All appropriate efforts will be made to avoid missing data, including monitoring of missingness and subject dropout rates by the PI and study manager or research coordinator biweekly during the study data collection phase. The research coordinator will investigate causes and remedies. For key analysis variables that have 15% or more missing values, we will analyze factors that are associated with having a missing value and perform a sensitivity analysis using multiple imputation to allow an unbiased analysis for all subjects.

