- **At risk of unintended pregnancy (UIP):** a subgroup of the full sample defined as having had sex with a man in the past 12 months who has not had a vasectomy and not currently seeking pregnancy. Outcomes related to contraception will be assessed in the subgroup at risk for UIP.
- **Considering pregnancy:** a subgroup of the full sample who are considering or ambivalent about pregnancy in the next few years. The exploratory preconception health behaviors outcomes will be assessed in this subgroup.

Description of the study populations: Provider, patient, and clinic leader participants will be described through summary statistics of demographic characteristics, and for providers, practice characteristics.

Aim 1 Primary Outcome: The analysis for our primary outcome of patient-provider discussion of reproductive planning with share decision making (SDM) will be assessed post-visit in **the full sample**. For our Aim 1 primary outcome analysis, we will use a mixed effects logistic regression model to test whether the odds of occurrence of reproductive planning with SDM is significantly different in the intervention versus control arm post-visit. In addition to estimating the odds ratio, we will also estimate the difference in predicted probabilities between the intervention and control group.

Covariates to be included in adjustment models are as follows:

- Study site (categorical)
- Clinic practice-type (binary) – Women’s Clinic Y/N
- Visit Type (virtual/telephone vs. in-person)
- Patient Age (categorical)
- Patient Race/ethnicity (categorical)
- Patient Household Income (categorical)
- Patient Marital Status (categorical)
- Patient Parity (categorical)
- Mental Health Diagnosis (one or more, binary)
- Medical Comorbidity (one or more, binary)

Aim 1 Secondary Outcomes: Secondary outcomes for Aim 1 will be assessed post-visit.

Secondary outcomes assessed **in the full sample** include provider-patient communication self-efficacy and reproductive planning knowledge. Secondary outcomes assessed **in the subgroup at risk of UIP** include contraceptive decisional conflict, values concordance, and contraceptive method decision. We will use a mixed effects logistic regression model to test whether these outcomes are different in the intervention versus control arm post-visit.

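### One logistic model is set for all five Aim 1 secondary outcomes with no scale or cut-point stated, so any that is a multi-level score would have to be split into yes/no

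*Combined protocol and SAP*

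**What the plan says.** Section 5.6 (Aim 1 Secondary Outcomes) names five outcomes, all measured after the visit. Those for the full sample "include provider-patient communication self-efficacy and reproductive planning knowledge". Those for the subgroup at risk of unintended pregnancy "include contraceptive decisional conflict, values concordance, and contraceptive method decision". One sentence then sets the analysis for all of them: "We will use a mixed effects logistic regression model to test whether these outcomes are different in the intervention versus control arm post-visit".

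Section 3.0 presents three of the five as "measures of contraceptive decision quality (knowledge, decisional conflict, values concordance", again without a scale. Section 5.5 points elsewhere for the items: "All survey questions assessed at each timepoint are provided in the attached Patient Survey Instruments (Attachment Q) and summarized below". The summary that follows gives no scoring, and it calls the knowledge outcome family planning knowledge where section 5.6 calls it reproductive planning knowledge.

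Other parts of section 5.6 are more specific. Nearly every adjustment covariate is labelled categorical or binary, and the exploratory goals-concordant outcomes are defined category by category. The general undertaking to check model assumptions supplies neither a cut-point nor an alternative model.

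**The concern.** An ordinary logistic model needs a binary response. Read as written, the plan therefore analyses self-efficacy, knowledge and decisional conflict as yes/no. These are graded ideas that are often measured with several items. For knowledge there is a hint in the Introduction (2.0), where the tool is meant to improve knowledge of fertility, contraception and preconception risks, which is more than one topic.

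If any of the three is a score, two things follow.

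- **Lost information.** A split treats everyone on the same side of the line as alike, which lowers power. The exploratory interaction tests in section 5.6 are built on the same models and would inherit the loss.
- **Analytic freedom.** With no cut-point stated, the result can depend on where the line is drawn once data have been seen.

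These outcomes matter because section 3.0 makes better discussions and decision quality the route by which MyPath is expected to improve behaviour and health.

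**Working it through.** **The plan's own figure.** The only sample size stated is for the binary primary outcome, in section 5.6. Inputs: control rate ("will be 50%, based on estimates from the nationally-representative VA ECUUN study"), target 70%, two-sided 5% error, 80% power, 30% non-use, a coefficient of 0.01 read as the intracluster correlation, clusters of 15, and 5% attrition.

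- Two proportions, 50% against 70%: 93 per arm.
- Non-use: 93 / (1 − 0.30)² = 189.8 per arm.
- Design effect: 1 + (15 − 1) × 0.01 = 1.14.
- Total: 2 × 189.8 × 1.14 / 0.95 = 455.5, rounded up to 456.

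The figure reproduces. It concerns the primary outcome only. No power, standard deviation or effect size is given for any Aim 1 secondary outcome, so what follows is illustration under stated assumptions.

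**General cost of a split.** Assume a normal score and a pure shift between arms. Cutting at quantile q, with normal density φ(z_q) at the cut, keeps a fraction φ(z_q)² / [q(1 − q)] of the information.

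- Median: 2/π = 0.637, about 64%.
- 80th percentile: 0.490.
- 90th percentile: 0.342.

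Starting from 80% power on the score, power after the split is Φ[(1.960 + 0.842) × √efficiency − 1.960].

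- Efficiency 0.637: Φ(0.275) = 60.8%.
- Efficiency 0.5: Φ(0.021) = 50.8%.

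**The same at this trial's size.** Assume also the full sample of 456, 5% attrition, and the 1.14 design effect for both forms of the outcome.

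- Effective number per arm: 228 × 0.95 / 1.14 = 190.
- Shift detectable with 80% power on the score: (1.960 + 0.842) × √(2/190) = 0.287 SD between the arms as randomised.

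That same shift, tested as yes/no with the cut placed on the control distribution:

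| Cut | Control vs intervention above the cut | Power | Total N for 80% power |
|---|---|---|---|
| Median | 50% vs 61.3% | 60% | about 725 |
| 80th percentile | 20% vs 29.0% | 53% | 864 |
| 90th percentile | 10% vs 16.0% | 41% | about 1,178 |

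Section 5.1 caps enrolment at 570, so more patients could not make up the loss. Decisional conflict is tested only in the subgroup at risk of unintended pregnancy, whose size is not given. The proportion of information lost does not depend on sample size, but absolute power there would be lower than in the table.

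For a measure that is binary by construction, the efficiency is 1 and the loss is zero.

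**The case against.** The strongest reply is that nobody reading these documents has seen the instruments. All five outcomes appear by name only. Each may be binary by construction, or Attachment Q may define its scoring. This stands, and it is why the point is conditional. It does not remove the point: Attachment Q is described as holding the survey questions, and section 5.6 itself neither says that the outcomes are binary nor fixes a threshold.

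A second reply is that a mixed logistic model on a pre-specified threshold is a valid test of a difference in proportions, which some readers prefer to a mean difference. This also stands. A reader might infer that the stated model is simply wrong; the documents do not support that. For a score it would be valid but probably less efficient, provided that the cut is fixed in advance. An ordinal logistic model would need no cut, but the plan does not name one.

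A third reply is that the percentages are not properties of this trial. That is correct. They assume a normal score and a pure shift, and the 80% starting point is borrowed, since the plan powers only the primary outcome.

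**Conclusion.** The point holds in conditional form. Section 5.6 applies one mixed logistic model to all five Aim 1 secondary outcomes and gives no scale, scoring or cut-point for self-efficacy, knowledge or decisional conflict. Any of them that is a multi-level score would have to be split. Under the assumptions above, a median split keeps about 64% of the information and takes 80% power to about 61%; more uneven cuts cost more.

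A reader might go further and conclude that these three outcomes must be cut and that information will be lost. The documents do not show this, because they give no scale for any of them. Nor do they show that values concordance and method decision are binary; method decision could have several categories. These are secondary outcomes, so the primary analysis and the 456 are untouched. The change is still worth making, because analysing a score as a score is the better method wherever a score exists.

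**What to change.** In section 5.6, under Aim 1 Secondary Outcomes, give the instrument, scoring and scale of each of the five outcomes, and replace the single-model sentence with a rule along these lines:

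- Any Aim 1 secondary outcome scored on a multi-item or multi-level scale is analysed primarily with a linear mixed model, or an ordinal mixed model if the score has a marked ceiling or few levels. The model has a provider random intercept and the same covariates, and the adjusted difference is reported.
- Mixed logistic regression is kept for outcomes that are binary by construction.
- A dichotomised version of a score is supportive only, with its cut-point fixed and justified before analysis.

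The rule should not presuppose which of the five are binary; the scoring statement settles that. If all five prove to be binary, one sentence saying so is enough.

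The cost is wording. No extra patients are needed and, subject to what Attachment Q contains, no new survey items. A mean or ordinal difference is somewhat harder to communicate than a proportion, which the supportive binary summary covers.

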Aim 2 Secondary Outcomes: Secondary outcomes for Aim 2, including continuous contraceptive use, consistent contraceptive use, and unintended pregnancy, will be assessed at 3- and 6-month follow up **in the subgroup at risk of UIP**. We will use a mixed effects logistic regression model to test whether outcomes differ between groups. For continuous and consistent contraceptive use outcomes, we will adjust for self-reported pre-study contraceptive use (measured at the post-visit survey).

Exploratory Preconception Health Behaviors: These outcomes will be assessed among a subgroup of study participants considering pregnancy in the next few years or who are ambivalent about pregnancy (unsure). Preconception risk factors will be measured at baseline and using medical record data, and behaviors to modify those risk factors will be assessed at post-visit, 3-months, and 6-months.

Exploratory Analyses of Interaction Effects: **For Aim 1 and 2 outcomes**, we will assess modification of the effect of assignment to the intervention by the following 4 pre-specified factors: age, race/ethnicity, visit modality (in-person or virtual) and clinic type (Women’s Health Clinic yes/no). We will assess evidence for effect modification by adding the effect modifier and its interaction with the treatment assignment indicator to the primary analysis models specified above.

Exploratory Analyses of Patient-Centered Contraceptive Outcomes: Recognizing that pregnancy intentions may fluctuate and participants in the subgroup at risk of UIP may decide that they wish to pursue pregnancy during the study timeframe, we will create “goals-concordant” measures for both continuous contraceptive use over 6 months and consistent contraceptive use at 6 months. Goals-concordant continuous contraceptive use will be defined as non-continuous use among women who desire pregnancy now; any continuous use outcome among women who are not trying but would be okay with pregnancy; and continuous use among women who desire pregnancy later, never, or who are not sure. Goals-concordant

consistent contraceptive use will be defined as no method or inconsistent use among women who desire pregnancy now; no method, inconsistent use or consistent use among women who are not trying but would be okay with pregnancy; and consistent contraceptive use among women who desire pregnancy later, never, or who are not sure.

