In addition, we will create a “goals-concordant” reproductive behaviors outcome at 6 months, combining consistent contraceptive use and folic acid supplementation. Goals-concordant reproductive behavior will be defined as taking folic acid among women who desire pregnancy now; taking folic acid or consistent contraceptive use among women who are not trying but would be okay with pregnancy or who are unsure; and consistent contraceptive use among women who desire pregnancy later or never.

Aim 3 – Analysis Plan

Quantitative analyses will involve both MyPath analytics data and estimated cost data and will provide summary statistics such as total cost estimates, means or medians (e.g., of time spent using the tool), and proportions (e.g., of participants who used the tool, or who used specific components of the tool), etc. These analyses will be descriptive.

The qualitative interviews will be recorded, transcribed, and analyzed. Transcripts will be analyzed using inductive and deductive content analysis, which will allow us to obtain specific information about implementation barriers and facilitators as well as capture unanticipated themes and previously unidentified factors[41]. We will (1) deductively develop *a priori* codes based on the specified RE-AIM domains in Table 8, and (2) inductively create emergent codes to capture data that do not fit *a priori* codes. Two trained coders will independently code all transcripts. For each group separately (Veterans, providers, clinic leaders), we will begin with an initial codebook using our *a priori* codes and then add codes as they emerge[42, 43]. To maintain the iterative process even as the final codebooks are applied, open codes will continue to be developed and added to the codebooks. Transcripts coded before addition of the new codes will be reexamined with the updated codebooks to ensure consistency. All analyses will be facilitated by use of ATLAS.ti software. Code output will be reviewed and discussed amongst the investigator team to identify common themes within and across groups.

Staff Analysis Responsibilities and Involvement:

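### The combined 6-month goals-concordant outcome scores women who want pregnancy now on folic acid alone, so it can credit contraceptive use that the companion measure counts as discordant

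*Combined protocol and SAP*

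**What the plan says.** Section 5.6, under *Exploratory Analyses of Patient-Centered Contraceptive Outcomes*, defines two goals-concordant classifications at 6 months that both use consistent contraceptive use.

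**Consistent-use measure (contraception only).** Goals-concordant "consistent contraceptive use will be defined as no method or inconsistent use among women who desire pregnancy now". For women who would be okay with pregnancy every pattern counts: "no method, inconsistent use or consistent use among women who are not trying but would be okay with pregnancy". For women whose goal is later, never or not sure, only consistent use counts. The continuous-use measure in the same paragraph also places unsure women with later and never.

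**Combined measure.** This is introduced as a goals-concordant "reproductive behaviors outcome at 6 months, combining consistent contraceptive use and folic acid supplementation". Its three categories are:
- pregnancy now: "Goals-concordant reproductive behavior will be defined as taking folic acid among women who desire pregnancy now";
- okay or unsure: "taking folic acid or consistent contraceptive use among women who are not trying but would be okay with pregnancy or who are unsure";
- later or never: "and consistent contraceptive use among women who desire pregnancy later or never".

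The plan gives no reason for leaving contraception out of the first category, or for moving unsure women to a different group.

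**The concern.** An outcome presented as combining two behaviours should not ignore one of them in the group where the plan has just said what that behaviour ought to be. For women who want pregnancy now, the consistent-use measure accepts only "no method or inconsistent use among women who desire pregnancy now". The combined measure sets no condition on contraception, so it can label as concordant a woman whose contraceptive behaviour the preceding paragraph labels contrary to her goal.

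The regrouping of unsure women is a separate and softer matter. Section 2.0 says MyPath is meant to improve knowledge of preconception health risks as well as contraception. If it raises folic acid use, the combined outcome can improve among unsure women with no change in their contraceptive use, while the consistent-use measure does not move. Part of any gap between the two results would then come from the definitions.

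**Working it through.** The plan states no figure to reproduce. The check is to apply both rules, as written, to every possible record.

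**Inputs (all from Section 5.6).** Five goals (now, okay, unsure, later, never); three levels of contraceptive use (none, inconsistent, consistent); folic acid yes or no. That gives 5 × 3 × 2 = 30 cells.

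**Rules.**

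| Goal | Consistent-use measure: concordant if | Combined measure: concordant if |
|---|---|---|
| Now | use is none or inconsistent | folic acid |
| Okay | always | folic acid or consistent use |
| Unsure | consistent use | folic acid or consistent use |
| Later, never | consistent use | consistent use |

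**Cells where the two disagree.**

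| Goal | Contraceptive use | Folic acid | Consistent-use measure | Combined measure |
|---|---|---|---|---|
| Now | none | no | concordant | discordant |
| Now | inconsistent | no | concordant | discordant |
| Okay | none | no | concordant | discordant |
| Okay | inconsistent | no | concordant | discordant |
| Now | consistent | yes | discordant | **concordant** |
| Unsure | none | yes | discordant | **concordant** |
| Unsure | inconsistent | yes | discordant | **concordant** |

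So 7 of 30 cells differ. Four are stricter in the combined measure, which is what adding a folic acid component should do. Three are more lenient: one comes from the missing contraceptive condition in the first category, and two come from the regrouping of unsure women. Later and never agree in every cell.

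**Effect of the changes.** Requiring folic acid and no consistent use in the first category removes the now/consistent/folic acid cell: 7 − 1 = 6 cells differ, 2 of them lenient. Also grouping unsure with later and never removes the two unsure cells: 6 − 2 = 4 cells differ, all from the added folic acid component.

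**How many women.** The documents give no 6-month distribution of goals, contraceptive use or folic acid use, so no count can be derived. For illustration only, assume 300 followed women at risk of unintended pregnancy.
- Unsure: assume 15–25% are unsure, 30–40% of them without consistent use, and 25–40% of those on folic acid. Then 0.15 × 0.30 × 0.25 = 1.1% to 0.25 × 0.40 × 0.40 = 4.0%, or about 3 to 12 women.
- Now: assume 5% want pregnancy now, 30% of them still use contraception consistently, and 25–40% of those take folic acid. Then 0.05 × 0.30 × 0.25 = 0.4% to 0.05 × 0.30 × 0.40 = 0.6%, or about 1 to 2 women. Doubling the 5% doubles the result.

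Every rate here is an assumption.

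**The case against.** The strongest reply is that the two measures address different constructs and need not agree. That accounts fully for the four stricter cells. It also goes a long way for unsure women: under *Analytic Subgroups*, Section 5.6 places women ambivalent about pregnancy in the considering-pregnancy subgroup and says "The exploratory preconception health behaviors outcomes will be assessed in this subgroup". A measure that includes folic acid can reasonably accept either preparation or prevention as fitting an unsure goal, whereas a contraception-only measure cannot credit preparation. The regrouping is therefore a defensible choice that lacks a stated reason, and it should not be called an error.

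The reply does not cover the first category. Adding folic acid does not explain why consistent contraception stops mattering for women who want pregnancy now. It is fair to say that this cell is probably close to empty, and that the companion measure still records the contraceptive behaviour.

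Three stronger readings are tempting, and the documents support none of them.
- *Folic acid values will be missing for women whose goals change after enrolment.* The subgroup rule in Section 5.6 is introduced as a limit on analysis. Section 5.5 lists preconception behaviours in the 3- and 6-month surveys without a subgroup limit, and the survey instrument (Attachment Q) is not available here. No request for an added survey item follows.
- *A difference between the two outcomes could not be interpreted.* Both rules are fully specified, so any divergence can be traced by tabulating goal, contraceptive use and folic acid.
- *The 5% in the attrition assumption caps the number of women wanting pregnancy now.* It is a planning allowance covering women who become pregnant or change to desiring pregnancy, and is not an upper bound.

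**Conclusion.** The point holds in a narrow form. By the plan's own standard, the first category of the combined outcome misclassifies a woman who wants pregnancy now, takes folic acid and uses contraception consistently. The different placement of unsure women may be intended, but it allows the two outcomes to separate for definitional reasons. The 7-of-30 and 3-of-30 cell counts follow from the text alone. The number of women cannot be computed; that it is small is a judgement resting on assumed rates. The outcome is exploratory, and the primary and secondary analyses and the sample size are unaffected. This is a worthwhile tidy-up and no threat to the trial's conclusions.

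**What to change.** Before analysis, make two changes in Section 5.6.

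1. Redefine the first category of the combined outcome so that a woman who desires pregnancy now is concordant only if she takes folic acid and uses either no method or a method inconsistently. This matches the consistent-use measure.
2. Report the combined outcome with unsure women grouped each way (with okay, and with later and never) as a sensitivity analysis. If the current grouping is intended, add one sentence giving the reason.

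The cost is one recoded variable and one extra tabulation. The recode needs contraceptive use among women who want pregnancy now, which the consistent-use measure already requires.
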